6.1 Efficacy Measures

6.1.1 Primary Efficacy Measures

- MAS-B of the principal muscle group (elbow or wrist)
- CGI by Physician (for US FDA only)

6.1.2 Secondary Efficacy Measures

- CGI by Physician (for non-US FDA analyses)
- MAS-B of the finger flexor muscle group
- Goal Attainment Scale (GAS) by Physician
- Modified Tardieu Scale (MTS) of the principal muscle group

6.2 Safety Measures

- Adverse events
- Physical examination
- Urine pregnancy tests (for all females of childbearing potential)
- Hematology and serum chemistry
- Vital signs (blood pressure, pulse rate, respiratory rate, and body temperature)
- Body weight
- C-SSRS (for patients \geq 6 years of age at day 1)

6.3 Examination Procedures, Tests, Equipment, and Techniques

The procedures are described in Attachment 12.1.

6.4 Other Study Supplies

The following study supplies will be provided by Allergan or a vendor contracted by Allergan:

- Laboratory kits for the collection and shipment of hematology, biochemistry, and urine samples (including pregnancy kits) will be provided by a vendor (eg, central laboratory) contracted by Allergan.
- Calibrated temperature recorder for monitoring drug storage refrigerator temperatures
- Syringe labels
- Goniometer
- Kilogram-only weight scale for selected sites (weight must be measured and collected in kilograms only)

The study sites will be responsible for providing the following supplies/equipment:

- Needles and syringes for study drug reconstitution and injection
- Sterile saline (0.9% without preservative) for study drug reconstitution
- Surgical gloves for study drug reconstitution
- [REDACTED]
- Access to a computer with internet connection (high-speed connection for eCRF completion)
- Standard 12-lead ECG
- Weight scale with height measure (if not supplied by Allergan)
- Centrifuge for processing lab samples
- Ultrasound and/or e-stimulation or EMG device for muscle localization techniques

6.5 Summary of Methods of Data Collection

An IVRS/IWRS will be used to screen, randomize, and manage study medication inventory. Data will be collected using eCRFs via a validated electronic data capture system (EDC). Source documents will be used and stored at the sites, and may include a patient's medical records, hospital charts, clinical charts, patient chart, copy of the EDC file, as well as the results of diagnostic tests such as laboratory tests, ultrasounds, x-rays, and ECGs. A central laboratory will be used for the analysis of all blood samples. For patients \geq 6 years of age at day 1, the C-SSRS will be collected as a clinical interview and the scores will be collected from the designated site staff using an electronic data collection method (eg, electronic tablet).

7. Statistical Procedures

The database will be locked when all patients have completed the study. A detailed analysis plan will be generated prior to the final database lock. All planned analyses will be performed after the database has been locked and randomization data released.

7.1 Analysis Populations

Safety data will be analyzed on the basis of all treated patients based on the treatment received, defined as the safety population. Efficacy data, demographics, and background information will be analyzed on the basis of the modified intent-to-treat (mITT) population, defined as all randomized patients with a valid MAS-B baseline score of the principle muscle group and at least one post-baseline measurement at weeks 2, 4, or 6 for the MAS-B of the principle muscle group and the CGI by Physician.

7.2 Collection and Derivation of Primary and Secondary Efficacy Assessments

At each scheduled office visit at weeks 2, 4, 6, 8, and 12, the patient's spasticity of the designated principal muscle group will be evaluated using the MAS-B. MAS-B scores of 0, 1, 1+, 2, 3, or 4 will be coded as grades of 0, 1, 2, 3, 4, or 5, respectively. The MAS-B grade change from baseline to each post-randomization office visit and the primary endpoint, average change at weeks 4 and 6 using the multiple imputation (MI) method, will be derived for each patient. Additionally, a responder status will be determined according to whether or not a patient has at least a 1-grade reduction from baseline on the MAS-B.

The secondary efficacy measure, CGI by Physician (for US FDA, CGI by Physician is a co-primary measure), will be measured at weeks 2, 4, 6, 8, and 12. CGI is a 9-point scale from -4 (very marked worsening) to +4 (very marked improvement). Each assessment is evaluated relative to the patient's baseline status obtained at day 1. The average of scores at weeks 4 and 6 using the MI method for missing values will be derived for CGI by Physician. Additionally, a responder status will be determined according to whether or not a patient has at least +1 score of CGI by Physician. The secondary efficacy measures of MAS-B of the finger flexor muscle group, GAS, and MTS will also be collected at scheduled office visits according to the Schedule of Visits and Procedures in Table 1. The difference between slow (R2) and fast (R1) range of motion (R2 - R1; see Attachment 12.1.11 for a detailed description of the MTS) and respective change from baseline to each posttreatment office visit on the MTS will be derived. The MI method is only intended for MAS-B scores of the principle muscle group and the CGI by Physician. Missing values for other variables will not be imputed.

7.2.1 Primary Efficacy Variables

The primary efficacy variable is the grade change from baseline in MAS-B of the principal muscle group. The primary efficacy endpoint will be the average grade change from baseline in the MAS-B of the principal muscle group at weeks 4 and 6. For US FDA only, the average grade change from baseline in the MAS-B of the principal muscle group and the average CGI by Physician are co-primary efficacy variables. Grade change from baseline in the MAS-B of the principal muscle group and the CGI by Physician will be analyzed as co-primary endpoints for the average of weeks 4 and 6 (see Section 7.7).

7.2.2 Secondary Efficacy Variables

The secondary efficacy variables are CGI by Physician (for non-US FDA analyses), the grade change of MAS-B of the finger flexors, GAS by Physician, and MTS. The secondary efficacy variables of CGI by Physician and the MAS-B change from baseline for finger flexors will be evaluated at weeks 2, 4, 6, 8, and 12. The MAS-B change from baseline for finger flexors will be analyzed using the subgroup of patients with wrist identified as the principal muscle group. Functional goals (active and passive) using GAS by Physician will be evaluated separately relative to baseline at weeks 8 and 12, and MTS including the difference between slow (R2) and fast (R1) range of motion (R2 - R1) as well as respective change from baseline on the MTS of the principal muscle group at weeks 2, 4, 6, 8, and 12. Additionally changes from baseline for each R1 and R2 at each assessment point will be evaluated. In addition to each timepoint, the average of the weeks 4 and 6 MAS-B change from baseline of the finger flexors and CGI by Physician will be analyzed.

7.3 Hypothesis and Methods of Analysis

7.3.1 Primary Efficacy Analyses

The primary efficacy analyses will be based on the mITT population. The primary analysis will be conducted for the average change from baseline in MAS-B score for the principal muscle group at weeks 4 and 6 using the MI method for missing values. The statistical null hypothesis is that both higher dose (6 U/kg) and lower dose (3 U/kg) have the same mean as placebo. The alternative hypothesis is that at least one study dose has a different mean than placebo. The hypothesis will be tested based on the least square (LS) mean differences from an analysis of covariance (ANCOVA) at a significance level of 0.05. The primary variable will be summarized by treatment group. The difference of LS means of each dose group and the placebo group from the ANCOVA model will be used to test the null hypothesis. The ANCOVA will be performed using the following model statement:

Primary variable = baseline MAS-B + age group + principal muscle group + treatment group + study center + previous botulinum toxin exposure, where age group and principal muscle group are represented by stratification categories (≤ 6 years and > 6 years for age group, elbow flexors and wrist flexors for designated principal muscle group). Baseline MAS-B grade is a continuous variable included as a covariate. Two tests will be performed based on the pairwise comparisons: 6 U/kg versus placebo and 3 U/kg versus placebo, each at a 0.05 significance level.

To control the type I error rate for the primary endpoint of the average change from baseline in MAS-B score of the principal muscle group at weeks 4 and 6, a gatekeeping approach will be used for this variable (Dmitrienko et al, 2005). Specifically, for the average of the grade change from baseline in MAS-B at weeks 4 and 6, the LS mean difference of 6 U/kg versus placebo from the ANCOVA will be tested first. If the test is not statistically significant at the level of 0.05, the test of the LS mean difference of 3 U/kg versus placebo will not be considered statistically significant regardless of its p value. Otherwise if the test for 6 U/kg versus placebo is statistically significant, then the test for 3 U/kg versus placebo will be evaluated based on its p value.

For sensitivity analysis purposes to supplement the primary analyses, Mixed Model Repeated Measures (MMRM) with an unstructured covariance matrix will be conducted. The model will include baseline MAS-B as a covariate and factors of age group, principal muscle group, treatment group, visit, treatment-by-visit interaction, study center, and previous botulinum toxin exposure. A summary of the percentage of missing MAS-B scores by visit will also be provided. Additional sensitivity analyses for the MAS-B changes from baseline at each assessment timepoint will also be performed using ANCOVA with the same model as specified above, and linear contrasts will be used to estimate the treatment differences between each study dose and placebo. The sensitivity analyses will be conducted using observed data.

In addition, the frequency distribution of the grade changes from baseline in the MAS-B, as well as the percentage of responders (with at least a 1-grade reduction in MAS-B), will be summarized by treatment group at each posttreatment office visit. A logistic regression analysis will also be performed on the responder status at each posttreatment visit with a covariate of baseline MAS-B and factors of age group, principal muscle group, treatment group, study center, and previous botulinum toxin exposure, if applicable. The additional analyses will be conducted using observed cases unless stated otherwise.

For US FDA only, CGI by Physician will be a co-primary variable (see Section 7.7 for description of analyses).

7.3.2 Secondary Efficacy Analyses

The observed cases will be used for secondary efficacy analyses unless stated otherwise. CGI by Physician will be rated at study weeks 2, 4, 6, 8, and 12. CGI by Physician will be summarized and analyzed by ANCOVA as the average of values at weeks 4 and 6 using the MI method for missing values, as well as at each assessment timepoint using observed cases. The frequency distribution of the CGI scores, as well as the percentage of responders (CGI score of at least +1), will be summarized by treatment group at each posttreatment timepoint. A logistic regression analysis will also be performed on the responder status at each posttreatment timepoint with factors age group, principal muscle group, treatment group, study center, and previous botulinum toxin exposure, if applicable.

The average grade change from baseline for weeks 4 and 6 in the MAS-B for finger flexor muscle groups will be summarized by treatment group and analyzed by ANCOVA using the subgroup of patients with wrist identified as the principal muscle group. The grade change from baseline in the MAS-B for finger flexor muscle groups at each timepoint will also be summarized by treatment group and analyzed by ANCOVA using the same subgroup. The ratings for each of the 2 goals using GAS at weeks 8 and 12 will be summarized by treatment group and analyzed by ANCOVA as specified in Section 7.3.1 to assess the treatment differences. For MTS, the difference between slow and fast motion (R2 - R1) and the individual R2 and R1 values in degrees for the principal muscle group, as well as the respective changes from baseline, will be summarized by treatment group and analyzed by ANCOVA.

[REDACTED]

[REDACTED]

[REDACTED]

[REDACTED]

[REDACTED]

[REDACTED]

[REDACTED]

7.3.4 Safety Analyses

Safety variables, including the incidence of adverse events, the incidence of suicide-related events using the C-SSRS (for patients \geq 6 years of age at day 1), laboratory test values and changes from baseline, as well as vital signs and their change from baseline, will be summarized by treatment group using the safety population. The Medical Dictionary for Regulatory Activities (MedDRA) nomenclature will be used to code adverse events and medical history. The incidence of adverse events (both pre-treatment events and treatment-emergent events) will be tabulated by primary system organ class and preferred term for each treatment group. Possible distant spread of toxin adverse events will be assessed using a standardized methodology.

Descriptive statistics will be presented for vital signs and numeric laboratory tests and the respective changes from baseline. All laboratory values will be presented by descriptive statistics. In addition, laboratory values outside the normal reference ranges for each patient at each applicable visit will be identified and evaluated against baseline via shift table analysis. Potentially clinically significant abnormal values may be identified or summarized descriptively.

7.4 Subgroup Analyses

Among the efficacy variables, the primary and selected secondary efficacy variables will be summarized by baseline MAS-B score (2 and > 2), age (≤ 6 years and > 6 years), designated principal muscle group, and previous exposure to botulinum toxin.

The analyses of adverse events will be presented by type of anesthesia, previous exposure to botulinum toxin, and age group, if appropriate.

7.5 Sample Size Calculation

Approximately 224 patients will be enrolled to ensure that at least 213 patients (71 per treatment group) will complete the study.

Using a 2-sample t-test, a significance level of 0.05, and the assumptions in Table 4, the power for MAS-B change from baseline is 86% (PASS, [Hintze, 2008](#)). The calculation is based on assumptions for the 6 U/kg group and the placebo group. Since there are 2 co-primary endpoints for the US FDA analysis, for the 6 U/kg group the power for CGI by Physician is calculated to be 94%, and the overall power for the US FDA co-primary endpoints will be at least 81%. The assumptions for MAS-B and CGI treatment differences were based on completed Studies 191622-008, BTOX-133/134/8051, BTOX-418/422-8051, BTX108509 and 112958, with standard deviation assumptions based on observed masked data from this ongoing study. The conservative overall power is calculated assuming that the MAS-B and CGI are independent. Note that the improvements in MAS-B were generally positively correlated with CGI scores based on completed adult spasticity studies.

Table 4 Sample Size Assumptions and Power Calculations

Endpoint	Average difference between 6 U/kg BOTOX group and placebo group at Weeks 4 and 6	Standard Deviation	Power
MAS-B Change from Baseline	-0.5	0.98	86%
CGI by Physician (Co-primary for US FDA Analysis)	0.6	1.02	94%
Overall Power			81%

CGI = Clinical Global Impression of Overall Change; MAS-B = Modified Ashworth Scale - Bohannon

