7.7.1 Primary Efficacy Analyses

There are 2 co-primary endpoints: the average grade change from baseline in the MAS-B of the principal muscle group at weeks 4 and 6 and the average CGI by Physician at weeks 4 and 6. For both co-primary endpoints, the statistical null hypothesis is that both the higher dose (6 U/kg) and the lower dose (3 U/kg) have the same mean as placebo. The alternative hypothesis is that at least one study dose has a different mean than placebo. In addition to the primary statistical analyses cited in Section 7.3.1 for the average grade change from baseline in MAS-B score of the principal muscle group at weeks 4 and 6, the average CGI by Physician at weeks 4 and 6 will be analyzed using the same statistical method (with the same ANCOVA model and the MI method).

The Hochberg procedure ([Hochberg and Tamhane, 1987](#)) will be used to control the family-wise type I error rate. With 2 doses and 2 co-primary endpoints in each dose, the maximum p value for the 2 co-primary endpoints in each dose will be used in the Hochberg procedure. We first define the following values:

- p11: p value for Botox 6 U/kg vs placebo comparing MAS-B
- p12: p value for Botox 3 U/kg vs placebo comparing MAS-B
- p21: p value for Botox 6 U/kg vs placebo comparing CGI
- p22: p value for Botox 3 U/kg vs placebo comparing CGI
- p1 = max(p11, p21), p2 = max(p12, p22).

p1 and p2 will be sorted in an increasing order to get $p(1) \leq p(2)$. The following decision rule will then be applied:

Step 1: If $p(2) \leq 0.05$, both doses are considered efficacious; otherwise go to step 2.

Step 2: If $p(1) \leq 0.025$, its corresponding dose is considered efficacious; otherwise go to step 3.

Step 3: Neither dose is considered efficacious.

For sensitivity analysis purposes to supplement the co-primary analyses, MMRM with unstructured covariance matrices will be conducted for the co-primary endpoints of MAS-B and CGI. The models will include a covariate of baseline MAS-B and factors of age group, principal muscle group, treatment group, visit, treatment-by-visit interaction, study center, and previous botulinum toxin exposure. A summary of the percentages of missing MAS-B and CGI scores by visit will also be provided. Additional sensitivity analyses for the MAS-B

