1.1 Primary Study Objectives and Design

The primary objective of the study is to evaluate the safety and efficacy of a single treatment of 2 doses (3 U/kg and 6 U/kg) of BOTOX with standardized occupational therapy (OT) in pediatric patients with upper limb spasticity.

This is a multicenter, randomized, double-blind, placebo-controlled, parallel-group, 12-week study evaluating 2 doses of BOTOX, 6 U/kg, 3 U/kg, and placebo with standardized OT for the treatment of monoplegic, hemiplegic, or triplegic children with upper limb spasticity due to cerebral palsy or stroke.

A centralized randomization scheme stratified by age group, principal muscle group, and baseline modified Ashworth Scale – Bohannon (MAS-B) will be used. Patients will be randomized to 1 of 3 treatment groups in a 1:1:1 ratio within each combination of strata. The stratification categories are as follows:

1. Age (≤ 6 years and > 6 years)
2. Designated principal muscle group (elbow flexors and wrist flexors)
3. Baseline (day 1) MAS-B score of the principal muscle group (MAS-B = 2 and MAS-B > 2)

There will be 1 treatment cycle in the study. The maximum study duration per patient will be approximately 16 weeks (including up to 4 weeks in the screening period). Patients will complete 8 study visits as follows: screening (week -4 to week -2), initiation of standardized OT (week -2), randomization and treatment visit (day 1), and post-injection follow-up visits at weeks 2, 4, 6, 8, and 12. All patients will receive weekly OT sessions from week 2 through week 11.

Patients who successfully complete this study without major protocol deviations (eg, non-compliance to protocol required procedures) will be given the option of enrolling in open-label extension Study 191622-105 if they meet eligibility criteria.

Sample size calculation and power consideration are presented in Section 7.5 of the study protocol.

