10.1 Primary Efficacy Analyses

There are 2 co-primary endpoints: the average grade change from baseline in the MAS-B of the principal muscle group at weeks 4 and 6 and the average CGI by Physician at weeks 4 and 6. For both co-primary endpoints, the statistical null hypothesis is that both the higher dose (6 U/kg) and the lower dose (3 U/kg) have the same mean as placebo. The alternative hypothesis is that at least one study dose has a different mean than placebo. In addition to the primary statistical analyses cited in Section 5.2.1 for the average grade change from baseline in MAS-B score of the principal muscle group at weeks 4 and 6, the average CGI by Physician at weeks 4 and 6 will be analyzed using the same statistical method with a same MMRM model in Section 5.3.1.

The Hochberg procedure ([Hochberg and Tamhane, 1987](#)) will be used to control the family-wise type I error rate. With 2 doses and 2 co-primary endpoints in each dose, the maximum p-value for the 2 co-primary endpoints in each dose will be used in the Hochberg procedure. We first define the following values:

p11: p value for Botox 6 U/kg vs placebo comparing MAS-B

p12: p value for Botox 3 U/kg vs placebo comparing MAS-B

p21: p value for Botox 6 U/kg vs placebo comparing CGI

p22: p value for Botox 3 U/kg vs placebo comparing CGI

$p1 = \max(p11, p21)$, $p2 = \max(p12, p22)$.

$p1$ and $p2$ will be sorted in an increasing order to get $p(1) \leq p(2)$. The following decision rule will then be applied:

Step 1: If $p(2) \leq 0.05$, both doses are considered efficacious; otherwise go to step 2.

Step 2: If $p(1) \leq 0.025$, its corresponding dose is considered efficacious; otherwise go to step 3.

Step 3: Neither dose is considered efficacious.

For sensitivity analysis purposes to supplement the co-primary analyses, ANCOVA using MI for missing values will be conducted for the co-primary endpoints of MAS-B and CGI. The model will include baseline MAS-B as a covariate and factors of age group, principal muscle group, treatment group, study center, and previous botulinum toxin exposure. A summary of the percentages of missing MAS-B and CGI scores by visit will also be provided. Additional sensitivity analyses for the MAS-B changes from baseline and CGI scores at each assessment timepoint will also be performed using the same ANCOVA with observed data, and linear contrasts will be used to estimate the treatment differences between each study dose and placebo.

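### The power of at least 81% stated for the US FDA co-primary endpoints ignores the Hochberg rule; under that rule power for 6 U/kg is about 70% to 77% (71 per arm, independent endpoints)

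*Protocol*

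**What the plan says.** Protocol Section 7.5 bases the calculation on 6 U/kg against placebo only: "Using a 2-sample t-test, a significance level of 0.05, and the assumptions in Table 4". Table 4 gives a MAS-B difference of -0.5 with SD 0.98 (power 86%) and a CGI difference of 0.6 with SD 1.02 (power 94%). The section concludes that "the overall power for the US FDA co-primary endpoints will be at least 81"%. The Protocol Summary repeats this.

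On how the two powers are combined, Section 7.5 says: "The conservative overall power is calculated assuming that the MAS-B and CGI are independent". It adds that "the improvements in MAS-B were generally positively correlated with CGI scores based on completed adult spasticity studies". It gives no correlation value and no 3 U/kg effect.

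The US FDA decision rule is in Protocol Section 7.7.1 and, in the same form, in SAP Section 10.1: "the maximum p-value for the 2 co-primary endpoints in each dose will be used in the Hochberg procedure". If the larger of the two per-dose values is at most 0.05, both doses succeed. Otherwise, if the smaller is at most 0.025, "its corresponding dose is considered efficacious; otherwise go to step 3".

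The SAP has no power calculation of its own. Its Section 1.1 states: "Sample size calculation and power consideration are presented in Section 7.5 of the study protocol".

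**The concern.** The power statement and the decision rule describe different tests. Section 7.5 lets 6 U/kg succeed whenever both of its p values are at most 0.05. Section 7.7.1 does not: 6 U/kg gets the 0.05 threshold only when 3 U/kg also passes both endpoints at 0.05, and otherwise needs 0.025 on both. The rule that does test 6 U/kg first at the full 0.05 is the gatekeeping procedure of Section 7.3.1, which serves the non-FDA MAS-B analysis.

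The Hochberg condition is stricter, so power for 6 U/kg must be lower than the product of the two unadjusted powers. Section 7.5 nevertheless presents that product as a minimum. The word conservative there refers to endpoint independence and does not cover the dose multiplicity.

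At stake is how the US result is read. A reader would put the chance of missing the assumed 6 U/kg effect at no more than 19%. If the US claim narrowly failed, that reader would underestimate how likely such a failure was by design.

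**Working it through.** **Inputs from the documents.** Two-sided 2-sample t-test; 71 per arm; differences 0.5 (SD 0.98) and 0.6 (SD 1.02); 1:1:1 allocation with a shared placebo arm (Protocol Sections 7.5 and 5.4); Hochberg on the per-dose maximum p value (Section 7.7.1). No covariate gain is included, because Section 7.5 specifies a t-test.

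**Inputs not in the documents (assumed and varied).** The 3 U/kg effect, from 0 to 100% of the 6 U/kg effect on both endpoints; the endpoint correlation, from 0 to 0.7; and the number analysed, 71 or about 74 per arm (224 / 3 = 74.7).

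**Step 1: reproduce the plan's figure.** The noncentrality parameter is difference / (SD × √(2/n)), with 2n − 2 = 140 df.

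- MAS-B: 0.5 / (0.98 × √(2/71)) = 3.04; power at 0.05 is 85.5%.
- CGI: 0.6 / (1.02 × √(2/71)) = 3.50; power at 0.05 is 93.6%.
- Product: 0.855 × 0.936 = 80.0%. With the rounded table values, 0.86 × 0.94 = 80.8%.

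The plan's 81% is therefore the unadjusted product for 6 U/kg at 0.05.

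**Step 2: the case where 3 U/kg does not help.** 6 U/kg must then reach 0.025 on both endpoints. Power at two-sided 0.025 is 78.0% (MAS-B) and 89.1% (CGI). The product is 0.780 × 0.891 = 69.5%. At 74 per arm it is 79.8% × 90.4%, or 72.2% before rounding the factors.

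**Step 3: the full rule.** With p1 the larger 6 U/kg p value and p2 the larger 3 U/kg p value, 6 U/kg succeeds if max(p1, p2) ≤ 0.05, or if p1 ≤ p2 and p1 ≤ 0.025. This was simulated with 1,000,000 trials per scenario, and each t statistic used the pooled variance of the two arms compared. Power to declare 6 U/kg efficacious (%):

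| n per arm | Endpoint correlation | 3 U/kg effect 0% | 50% | 75% | 100% |
|---|---|---|---|---|---|
| 71 | 0 | 69.4 | 70.1 | 73.0 | 77.2 |
| 71 | 0.3 | 71.3 | 72.1 | 74.8 | 78.5 |
| 71 | 0.5 | 72.9 | 73.7 | 76.2 | 79.6 |
| 71 | 0.7 | 74.8 | 75.7 | 78.1 | 81.1 |
| 74 | 0 | 72.1 | 72.9 | 75.6 | 79.5 |
| 74 | 0.5 | 75.2 | 76.0 | 78.4 | 81.7 |
| 74 | 0.7 | 77.0 | 77.8 | 80.0 | 83.0 |

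The first cell agrees with the exact 69.5% of Step 2 within simulation error.

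**Step 4: compare like with like.** On the same t-test basis the unadjusted figure is 80.0%. With 71 per arm and independent endpoints, the Hochberg rule therefore costs between 80.0 − 77.2 = 2.8 and 80.0 − 69.5 = 10.5 percentage points. The chance of missing the assumed 6 U/kg effect is 22.8% to 30.5%.

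**The case against.** **The basis is disclosed.** Section 7.5 names the test, the 0.05 level, the 6 U/kg comparison and the independence assumption, and the multiplication is correct. That is true. But the product is then offered as a minimum for the US FDA endpoints, and those are decided by another rule.

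**The 3 U/kg effect is not the plan's.** This stands: the spread within each row of the table comes from an assumed quantity. A power figure under this Hochberg rule cannot be given without one, and the plan supplies none.

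**Independence and 71 per arm are pessimistic.** Section 7.5 reports positive correlation in adult studies. The mITT definition asks only for "at least one post-baseline measurement at weeks 2, 4, or 6" on MAS-B and CGI along with a valid baseline MAS-B, so more than 71 per arm may be analysed. Both points raise power, as the table shows. Within those scenarios, 81% is reached only when the doses are equally effective and the correlation is 0.7 (71 per arm) or at least 0.5 (74 per arm).

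**Overall power could mean success of at least one dose.** The alternative hypothesis in Section 7.7.1 is worded that way. On that reading, with 71 per arm and independent endpoints, power runs from about 70% (no 3 U/kg effect) to about 86% (equal effects), so 81% is still not a minimum. Section 7.5 also ties its calculation to 6 U/kg.

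**The SDs come from masked data.** If they were pooled across arms, which the protocol does not say, they contain between-arm variance and overstate the within-arm SD. For MAS-B with no 3 U/kg effect, the variance of the arm means (0, 0, 0.5) is 0.056, and √(0.98² − 0.056) = 0.95. Across the assumed 3 U/kg effects the SDs would be 0.95–0.96 and 0.98–0.99. Power would be about 73% to 81% (71 per arm, independent) or 79% to 85% (74 per arm, correlation 0.5). The shortfall shrinks, but 81% is still not guaranteed. Adjustment for baseline or the SAP's repeated-measures model could also change power, by an amount the documents do not give.

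**Conclusion.** The concern holds. The 81% applies to 6 U/kg tested at an unadjusted 0.05, and the plan does not use that rule for the US claim. Under the plan's Hochberg rule, power to declare 6 U/kg efficacious is about 70% to 77% with the plan's differences and SDs, a 2-sample t-test, 71 per arm, independent endpoints and a 3 U/kg effect between 0 and 100% of the 6 U/kg effect. The lower end applies for any 3 U/kg effect up to about half that of 6 U/kg. Higher correlation, more analysed patients or smaller within-arm SDs would narrow the gap, and favourable combinations close it, but none of these is fixed by the documents. The description of at least 81% is therefore wrong as written. This is a fault in the power statement only: type I error control is sound, and the 86% for the non-FDA MAS-B analysis is unaffected.

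**What to change.** In Protocol Section 7.5, Table 4 and the Protocol Summary, replace the overall power with power under the Section 7.7.1 rule, and state the assumed 3 U/kg effect, endpoint correlation and number per arm. Suggested text:

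*Under the Hochberg rule of Section 7.7.1, with a 2-sample t-test, 71 patients per group and independent endpoints, power to declare 6 U/kg efficacious on both co-primary endpoints is about 70% to 77% for a 3 U/kg effect of 0 to 100% of the 6 U/kg effect.*

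The 81% may stay beside it if it is labelled as the product of the two powers at 0.05 before adjustment for two doses. If the protocol will not be amended again, put the statement in SAP Section 1.1, which now only refers back to Section 7.5.

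The cost is one recalculation and wording in three places (or one sentence in the SAP), and a less favourable stated power. The testing procedure and enrolment stay as they are.
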